5.12 Standard Tests and Procedures

The required schedule for subject treatments and evaluations is summarized in Table 5-1.

Table 5-1 Schedule of Treatments and Evaluations

	Pre-Procedure		Ablation Procedure ¹	Discharge	Phone Call	Phone/ Office visit	Follow-Up Visits					Unscheduled Visit
	Screening / Baseline				7-9 Days	1 Month +/- 1 wks.	3 Month +/- 1 wks.	6 Month +/- 2 wks.	9 Month +/- 4 wks.	12 Month +/- 4 wks.	15 Month +/- 4 wks.	
Visit no.	1	2	3	4	5	6	7	8	9	10	11	12
Informed consent ¹	X											
Inclusion & exclusion criteria	X											
Demographics	X											
Medical history / Hospitalization history	X				X	X	X	X	X	X	X	X
Arrhythmias	X [history]			X	X	X	X	X	X	X	X	X
NIH Stroke Scale ¹²		X		X ¹²								
ECG		X		X				X	X	X	X	X
NYHA		X										
CCS-SAF		X						X	X	X	X	
QOL assessment ²		X						X	X	X	X	
Pregnancy test ³		X										
LA thrombus Imaging ⁴			X									
TTE ⁵		X ⁵		X ¹⁶								
Ablation assessments			X									
Holter monitor (24 hr)		X optional						X		X	X	
TTM monitoring ^{13,14}								X ^{13,14}	X ^{13,14}	X ^{13,14}	X ^{13,14}	

	Pre-Procedure		Discharge	Phone Call	Phone/Office visit	Follow-Up Visits						Unscheduled Visit
	Screening / Baseline	Ablation Procedure ¹				7-9 Days	1 Month +/- 1 wks.	3 Month +/- 1 wks.	6 Month +/- 2 wks.	9 Month +/- 4 wks.	12 Month +/- 4 wks.	
Visit no.	1	2	3	4	5	6	7	8	9	10	11	12
Device deficiency			X									
Concomitant medications ⁶		X	X	X	X	X	X	X	X	X	X	X
Health Economic Data Collection ⁷				X ⁷	X ⁷	X ⁷	X ⁷	X ⁷	X ⁷	X ⁷	X ⁷	X ⁷
Adverse events ^{8,9}	X	X	X	X	X ¹⁰	X ¹⁰	X	X	X	X	X	X
PV stenosis imaging assessment ¹¹					X ¹¹	X ¹¹	X ¹¹	X ¹¹	X ¹¹	X ¹¹	X ¹¹	X ¹¹
AF recurrence								X	X	X	X	X
End-of study follow-up											X ¹⁵	

¹ Initial ablation procedure should be done within 30 days of consent.

² Quality of life tools (AFEQT and Symptom and Severity Checklist)

³ Pregnancy test must be done on pre-menopausal women only, within 24 hours of the procedure.

⁴ Section 5.3 of the protocol should be followed when determining if a subject should undergo imaging for the presence of LA Thrombus.

⁵ Imaging TTE to determine the atrial size (if the subject has undergone an imaging procedure within the last 6 months where the atrial size was assessed, the pre-procedure imaging assessment is not required)

⁶ Concomitant medications: only cardiac related (anti-arrhythmia drugs, anticoagulation regimen, etc.)

⁷ Health Economic Data for hospitalizations (UB04), ER visits and outpatient visits, if any

⁸ AEs collected once consent has been signed

⁹ If AE results in Hospitalization health economic data collection is required

¹⁰ Collected via phone follow-up

¹¹ PV imaging (CT/MRI) for subjects who have symptoms suggestive of PV stenosis

¹² Performed prior to hospital discharge or 24 hours after the procedure, whichever is later or any time after the subject experiences a CVA/Stroke, perform Neuro consult as needed Refer to section 6.2.1 for additional details.

¹³ Asymptomatic TTM: should be recorded monthly (i.e. at months 7, 8, 9, 10, 11, 12, 13, 14, 15) and transmitted to the Core Lab. Refer to section 5.15.

¹⁴ TTM: all symptomatic cardiac episodes should be recorded and transmitted at the time the event occurs. Refer to section 5.15.

¹⁵ 15-month visit or last completed visit

¹⁶ Subjects who develop symptoms suggestive of pericardial effusion and/or pericarditis should undergo a transthoracic echocardiogram (TTE) to assess the pericardium

5.13 Study Medications

The following medications are recommended/required (as indicated) for subjects undergoing a study catheter ablation for AF.

5.13.1 Anticoagulation Medications

- **Medication Prior to AF Ablation Procedure**
 - Subject should be placed on systemic anticoagulation therapy for at least 3 weeks prior to the AF ablation procedure.
- **Medication During AF Ablation Procedure**
 - **Heparin:** to achieve an activated clotting time (ACT) of ≥ 325 seconds during the AF ablation procedure in the left atrium.
 - ACT levels **MUST** be checked prior to administering RF energy and rechecked every 15-30 minutes during the ablation procedure in the left atrium to ensure ACT ≥ 325 seconds. All recordings must be documented in the medical records as source documentation.
 - **Adenosine:** 20mg bolus to confirm PV isolation; rule out dormant conduction
 - **Isoproterenol:** recommended if pacing maneuvers are not performed, to achieve a ≥ 20 beats per minute increase in heart rate to induce AF upon completion of the ablation procedure is (recommended dose range is 2-20 mcg/min).
- **Medication Following AF Ablation Procedure**
 - It is recommended that physicians follow the relevant recommendations from the 2012 HRS/EHRA/ECAS Expert Consensus Statement on Catheter and Surgical Ablation of AF.⁴ All anticoagulation therapy will be recorded on the appropriate case report form.
 - All subjects **MUST** be maintained on systemic oral anticoagulation therapy for 2 months post-procedure. Reinitiate oral anticoagulation therapy within 6 hours post procedure).
 - Systemic oral anticoagulation is achieved using INR- dose adjusted warfarin (INR should be maintained between 2.0 and 3.0, inclusive), direct thrombin inhibitor, or factor Xa inhibitor.
 - At 2 months post-procedure, decision regarding continuation of systemic anti-coagulation agents is based on the subject risk for thrombo-embolism. Systemic oral anticoagulation is strongly encouraged to be continued beyond 2 months post ablation in subjects with CHADS₂ score > 1 .

5.14 Antiarrhythmic Drug (AAD) Management

5.14.1 Definitions

- **Antiarrhythmic drugs (AADs)**
 - The study protocol will classify and analyze the following:

- Class I drugs (e.g., flecainide, propafenone, disopyramide, etc.)
- Class III drugs (e.g., amiodarone, dronedarone, dofetilide, etc.)

- **Previously Failed AAD**

Any AAD that a subject has ever taken for the treatment of his/her AF, prior to enrollment, is considered a “previously failed AAD” if it meets both of the following conditions:

- prior to enrollment, the AAD was ineffective in controlling the subject’s AF or produced intolerable side effects leading to its discontinuation;
- the AAD is administered for AF

- **New AAD**

ANY AAD that was never taken for the treatment of AF prior to enrollment is considered a “new AAD” if the drug is administered to treat an “atrial tachyarrhythmia” post-enrollment.

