4.0 STUDY ENDPOINTS

4.1 Primary Endpoints

4.1.1 Primary Effectiveness Endpoint

The primary effectiveness endpoint is defined as the freedom from documented atrial fibrillation, atrial flutter and atrial tachycardia (AF/AFL/AT) (hereinafter collectively referred to as "atrial tachyarrhythmias") recurrence (episodes ≥ 30 secs on Holter recordings/TTM or continuously recorded on the standard 12-leads ECG) during the evaluation period (Day 181-450) and freedom from the following failure modes:

- Acute procedural failure, including:
 - Failure to confirm entrance block in all pulmonary veins post-procedure,
 - Use of a non-study catheter to treat the study arrhythmia for the initial ablation procedure.

Device deficiency of a non-investigational device leading to the use of a non-study catheter (i.e., Stockert 70, SMARTABLATE™ RF Generator and COOLFLOW® Pump, SMARTABLATE™ Irrigation Pump), during the AF procedure will not be considered an acute failure.

- Non-study catheter failure:
 - Use of a non-study catheter to treat the study arrhythmia for repeat ablation procedure during the 3-Month Medication Adjustment or 3-Month Therapy Consolidation Periods.
- Repeat ablation failure, including:
 - > 2 repeat ablation procedures during the 3-Month Medication Adjustment Period / 3-Month Therapy Consolidation Period (Day 0-180) after the index procedure.
 - Any repeat ablation procedure during the Evaluation Period.

Refer to section 5.18 for details.

- AAD failure: Taking a new AAD or a previously failed AAD at a greater than the highest ineffective historical dose for AF during the evaluation period (refer to section 5.14 for details).
- Surgical failure: Undergoing surgical AF ablation or AF surgery any time after the index procedure.

In summary, effectiveness success is defined as freedom from atrial tachyarrhythmia during the Evaluation Period, off or on a previously failed AAD, and not exceeding 2 repeat ablation procedures for an atrial tachyarrhythmia during the 3-Month Medication Adjustment and 3-Month Therapy Consolidation Periods.

This study is designed to compare the primary effectiveness of the investigational device to a pre-determined performance goal of 40%, which is indicated as the minimum acceptable success rate at 12 months for a persistent AF population in the 2012 HRS

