5.14.2 AAD Usage and Primary Effectiveness Classification

- **AAD Therapy in the 3-Month Medication Adjustment Period (Day 0-90) and 3-Month Therapy Consolidation Period (Day 91-180):**

During this interval, subjects may receive new AADs or previously failed AADs without affecting their primary effectiveness classification.

- **AAD Therapy in the Effectiveness Evaluation Period (Day 181-450):**

- New AADs:

- Continued beyond the 3-Month Medication Adjustment Period / 3-Month Therapy Consolidation Period for treating “atrial tachyarrhythmia” will result in the subject being classified as a primary effectiveness failure.

- A new AAD for an “atrial tachyarrhythmia” started in the evaluation period will result in the affected subject being classified as a primary effectiveness failure.

- Previously failed AADs:

- Started in or continued from the 3-Month Medication Adjustment Period / 3-Month Therapy Consolidation Period and remaining at the same or lower dose than the highest ineffective historical dose will not result in the affected subject being classified as a primary effectiveness failure.

- Taking a previously failed AAD at a dose greater than the highest ineffective historical dose for AF during the evaluation period will result in the affected subject being classified as a primary effectiveness failure.

Table 5-2 illustrates the corresponding classifications based on AAD therapy administered in the 3-Month Medication Adjustment Period / 3-Month Therapy Consolidation Period and the evaluation period.

Table 5-2 AAD Usage and Impact on Primary Effectiveness Classification

AAD Medication		
	Medication Adjustment / Therapy Consolidation Period: (Day 0-180):	Evaluation Period: (Day 181-450)
New AAD	if initiated but stopped by Day 180; subject will not be classified as a primary effectiveness failure.	if initiated; subject will be classified as a primary effectiveness failure. if initiated during Medication Adjustment/Therapy Consolidation period and continued past 180-days post-ablation; subject will be classified as a primary effectiveness failure.

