### **6 Study Endpoints**

#### **6.1 Primary Endpoints and Associated Hypotheses**

##### **6.1.1 Primary Effectiveness Endpoint**

The primary effectiveness endpoint is defined as achieving effectiveness success after undergoing an RF ablation procedure using the THERMOCOOL® SMARTTOUCH™ SF catheter.

The null and alternative hypotheses are:

*Hypothesis:*  $H_0: P_E \leq 0.40$

$H_a: P_E > 0.40$

where  $P_E$  is the proportion of subjects who meet the effectiveness success criteria at 15 months follow-up

A subject has reached the effectiveness success if the subject is free from documented atrial tachyarrhythmia, including atrial fibrillation, atrial flutter and atrial tachycardia (AF/AFL/AT), recurrence (episodes  $\geq 30$  secs on Holter recordings/TTM or continuously recorded on the standard 12-leads ECG) during the evaluation period (Day 181-450) and free from the following failure modes:

- Acute procedural failure, including
  - Failure to confirm entrance block in all pulmonary veins post-procedure,
  - Use of a non-study catheter to treat the study arrhythmia for initial ablation,

- Non-study catheter failure while treating the study arrhythmia for repeat ablation procedure during the 3-Month Medication Adjustment or 3-Month Therapy Consolidation Period
- Repeat ablation failure, including
  - >2 repeat ablation procedures during the 3-Month Medication Adjustment Period / 3-Month Therapy Consolidation Period (Day 0-180) after the index procedure,
  - Any repeat ablation procedure during the evaluation period.
- AAD failure: Taking a new AAD or a previously failed AAD at a greater than the highest ineffective historical dose for AF during the evaluation period.
- Surgical failure: Undergoing surgical AF ablation or AF surgery any time after the index procedure.

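### An antiarrhythmic drug (AAD) that worked before enrollment is neither new nor previously failed, so the failure list and the success summary score the same subject differently

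*Protocol*

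**What the plan says.** Protocol 5.14.1 sets up two classes of Class I/III drug.

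- **New AAD.** "ANY AAD that was never taken for the treatment of AF prior to enrollment is considered a" new AAD, if it is then given for an atrial tachyarrhythmia after enrollment.
- **Previously failed AAD.** A drug given for AF before enrollment that did not control the AF "or produced intolerable side effects leading to its discontinuation".

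The failure mode in Protocol 4.1.1 uses exactly these classes: "Taking a new AAD or a previously failed AAD at a greater than the highest ineffective historical dose for AF during the evaluation period". SAP 6.1.1 repeats it: "AAD failure: Taking a new AAD or a previously failed AAD at a greater than the highest ineffective historical dose for AF during the evaluation". Protocol 5.14.2 adds that a previously failed drug "remaining at the same or lower dose than the highest ineffective historical dose will not result" in failure. Table 5-2 has rows for the same two classes and no third.

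Protocol 4.1.1 closes with a summary that is not in the SAP: "effectiveness success is defined as freedom from atrial tachyarrhythmia during the Evaluation Period, off or on a previously failed AAD", with a limit on repeat ablations.

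Inclusion criterion 2 (Protocol 3.1.1) asks for at least one failed or not-tolerated AAD. It says nothing about any other AAD the subject has taken.

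**The concern.** The two classes do not exhaust the possible drug histories. Take a subject who failed one drug, was then held in sinus rhythm on a second drug started before consent, was ablated, and stayed on the second drug through Day 450. The second drug was taken before enrollment, so it is not new. It was neither ineffective nor stopped, so it is not previously failed. The same holds for a drug that worked, was poorly tolerated, but was never stopped.

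No listed failure mode applies to this subject, at any dose. Yet the summary does not admit the subject as a success. The primary endpoint then has two answers for one subject.

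This matters because the trial is unblinded, has a single arm, and is tested against a fixed 40% goal. There is no control arm in which the drug effect would also appear. If the list alone is applied, the error can only raise the success rate. The sensitivity analyses in SAP 10.4.3 concern missing data, and the additional subgroup analyses in SAP 10.4.4.4 are optional and name no AAD factor. No planned analysis would show the effect.

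**Working it through.** **Step 1: classify each pre-enrollment history, for a drug taken for AF in Day 181-450.**

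| History before enrollment | Class (5.14.1) | Failure list (4.1.1, 5.14.2, Table 5-2, SAP 6.1.1) | Summary (4.1.1) |
|---|---|---|---|
| Never taken for AF | New | Failure | Not a success |
| Ineffective, now at or below highest ineffective dose | Previously failed | Not a failure | Success allowed |
| Ineffective, now above that dose | Previously failed | Failure | Silent on dose |
| Stopped only for intolerance | Previously failed | Dose test has no reference dose | Success allowed |
| Neither ineffective nor stopped for intolerance | None | Not a failure | Not a success |

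The last row is the conflict. The fourth row is a different defect: no contradiction with the summary, but a dose limit that cannot be evaluated.

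**Step 2: can the last row occur?** Yes. One failed or not-tolerated drug is enough for entry, and the two ECGs that may document continuous AF can be up to 365 days old at enrollment. A subject can therefore qualify and be in sinus rhythm on another drug at consent.

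**Step 3: reproduce the plan's figures.** Inputs are n = 330, goal 40% and expected rate 50% (Protocol 7.4, SAP 9.1), with success if the exact two-sided 95% lower limit exceeds 40% (Protocol 7.2.1, SAP 10.4.1).

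- The smallest passing count is the smallest x with P(X ≥ x | 330, 0.40) ≤ 0.025. This is x = 151, and 151/330 = 45.8%.
- Exact one-sided type I error: P(X ≥ 151 | 330, 0.40) = 0.0193.
- Power: P(X ≥ 151 | 330, 0.50) = 0.945, consistent with the stated minimum of 90%.
- Enrollment: 330/0.90 = 366.7, rounded up to 367, as stated.

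**Step 4: margin at the planning rate.** Expected successes are 0.50 × 330 = 165, which is 165 − 151 = 14 above the threshold. Rescoring 15 subjects (15/330 = 4.5%) leaves 150 and the goal is missed.

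**Step 5: effect of an assumed share m of evaluable subjects.** The documents give no value for m.

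- Column A: the true rate without affected subjects is 40%, and m is the share counted as successes solely because of the drug. Chance of passing = P(X ≥ 151 | 330, 0.40 + m).
- Column B: the planned 50% already included such subjects, and m is the share rescored as failures. Power = P(X ≥ 151 | 330, 0.50 − m).

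| m | A: chance of passing | B: power on the stricter count |
|---|---|---|
| 0% | 1.9% | 94.5% |
| 1% | 4.5% | 89.1% |
| 2% | 9.3% | 80.8% |
| 3% | 16.9% | 69.4% |
| 5% | 41.2% | 41.2% |

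The two entries at 5% agree because both put the counted rate at 45%.

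**The case against.** The best case for the plan has four parts.

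- **The group is probably small.** Subjects must be drug refractory with documented continuous AF, and Protocol 4.1.2 expects many to be in AF at the procedure. A drug being taken while the subject is in AF is evidently ineffective, hence previously failed. This stands as an argument about frequency. It does not remove the conflict, since eligibility allows the case.
- **The drafters may have meant the classes to be exhaustive, and the protocol summary may govern.** SAP section 1 says its methods rest on the protocol. So it cannot be asserted that the analysis would follow the lenient reading. But neither document says which text prevails, and someone programming from SAP 6.1.1 would see only the list.
- **Intolerance counts as drug failure by design.** A reader might infer that drugs stopped only for intolerance also contradict the summary, or that they can be resumed with no failure possible. The documents support neither. Protocol 5.14.1 makes such drugs previously failed, and the summary allows success on them. The exemption in 5.14.2 is tied to a reference dose that these drugs lack, so the result is undetermined rather than lenient. Moving them all to the new-AAD rule would override a stated choice.
- **Text may be missing.** The previously failed row of Table 5-2 carries an asterisk with no visible footnote, possibly lost from the PDF. It could bear on the dose reference. It would not change the wording of 4.1.1, 5.14.1 or SAP 6.1.1.

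**Conclusion.** The gap holds for one kind of history: a drug taken for AF before enrollment that was neither ineffective nor stopped for intolerance. Its use in Day 181-450 is not a failure under the list and not a success under the summary. Under SAP 6.1.1 as written it can be scored in the device's favor.

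The size is unknown. The range in the working rests on three assumptions: 330 evaluable subjects, a true rate of 40% without the affected subjects, and an assumed share whose success depends only on the drug. Subjects who would have stayed free of arrhythmia without the drug do not inflate the device effect. At 1% to 3% the chance of passing is 4.5% to 16.9%, against 1.9% with none; it reaches 41.2% only at 5%. A reader might infer that the gap would decide the trial; with no share in the documents, that cannot be said.

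For drugs stopped only for intolerance the finding is narrower: the dose reference is undefined. The sample size of 330 evaluable and 367 enrolled is not in question. This is a clarification of the primary endpoint to settle before outcomes are analyzed, held with moderate confidence as to its practical effect.

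**What to change.** **Scoring rule.** Reconcile Protocol 4.1.1, 5.14.1, 5.14.2 with Table 5-2, and SAP 6.1.1 by carrying the summary's condition into the failure list. A subject who takes, for an atrial tachyarrhythmia in Day 181-450, a Class I/III AAD that is not previously failed is then scored as a primary effectiveness failure. This changes scoring only and has no bearing on what may be prescribed.

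**Dose reference.** For drugs stopped only for intolerance, the same sections must be reconciled, because the highest ineffective dose does not exist for them. The sponsor should state how the dose test is scored in that case. No particular rule is proposed here.

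**Cost.** A few sentences in each document and a row in Table 5-2. Failed AADs and cardiac medications are already recorded at baseline (Protocol 5.3) and follow-up (Protocol 5.11), so no new data are needed for the scoring rule. The downside is a success rate that may be lower, since the rule also rescores affected subjects who would have done well without the drug. If the planned 50% included such subjects, power falls as in column B of the working.

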5.14.2 AAD Usage and Primary Effectiveness Classification

- **AAD Therapy in the 3-Month Medication Adjustment Period (Day 0-90) and 3-Month Therapy Consolidation Period (Day 91-180):**

During this interval, subjects may receive new AADs or previously failed AADs without affecting their primary effectiveness classification.

- **AAD Therapy in the Effectiveness Evaluation Period (Day 181-450):**

- New AADs:

- Continued beyond the 3-Month Medication Adjustment Period / 3-Month Therapy Consolidation Period for treating “atrial tachyarrhythmia” will result in the subject being classified as a primary effectiveness failure.

- A new AAD for an “atrial tachyarrhythmia” started in the evaluation period will result in the affected subject being classified as a primary effectiveness failure.

- Previously failed AADs:

- Started in or continued from the 3-Month Medication Adjustment Period / 3-Month Therapy Consolidation Period and remaining at the same or lower dose than the highest ineffective historical dose will not result in the affected subject being classified as a primary effectiveness failure.

- Taking a previously failed AAD at a dose greater than the highest ineffective historical dose for AF during the evaluation period will result in the affected subject being classified as a primary effectiveness failure.

Table 5-2 illustrates the corresponding classifications based on AAD therapy administered in the 3-Month Medication Adjustment Period / 3-Month Therapy Consolidation Period and the evaluation period.

Table 5-2 AAD Usage and Impact on Primary Effectiveness Classification

AAD Medication		
	Medication Adjustment / Therapy Consolidation Period: (Day 0-180):	Evaluation Period: (Day 181-450)
New AAD	if initiated but stopped by Day 180; subject will not be classified as a primary effectiveness failure.	if initiated; subject will be classified as a primary effectiveness failure. if initiated during Medication Adjustment/Therapy Consolidation period and continued past 180-days post-ablation; subject will be classified as a primary effectiveness failure.
Previously failed AAD*	if initiated at same or lower dose as previous prescription; subject will not be classified as a primary effectiveness failure. if continued (from prior to study enrollment); subject will not be classified as a primary effectiveness failure.	if initiated and prescribed at the same or a lower than the highest ineffective historical dose; subject will not be classified as a primary effectiveness failure. if continued (after initiation in medication adjustment/therapy consolidation period) and prescribed at the same or a lower than the highest ineffective historical dose after 180 days of the initial ablation. Subject will not be classified as a primary effectiveness failure if increased to dose greater than the highest ineffective historical dose, subject will be classified as primary effectiveness failure

